Further patient data that will be analyzed as secondary outcome measures at 2 and 6 weeks are adherence to allocated treatment and adverse events related to IPC. Adverse events (binary) that will be registered are 1) Any damage to the skin of the legs including infection. 2) Any reasons for prematurely stopping the IPC. 3) Any fall associated with significant injury occurring within 6 weeks of enrollment. The frequency of the adverse events of each group will be presented⁹.

Health economic analyses, together with Karolinska Institutet, LIME, Med. dr. [name], of the trial treatment effects will involve a within-trial evaluation of cost effectiveness integrated into a decision-analytic model of longer run costs and health effects.

Study Design (PICO)

“STOP leg clots” is an international, multicentre prospective randomized, controlled, parallel group trial with blinded assessment of the outcome. The allocation ratio is 1:1. The study has an Ethical review board approval 2016/1753-31 and is registered at clinicaltrials.gov.

Patients: At least 20 hospitals in a minimum of twelve regions have accepted to participate, and this captures a study population, which is representative of Sweden. The included patients, ATR and ankle fractures, are representative of, and constitute a large part of the population with lower limb immobilization. Moreover, patients with ATR and AF have

demonstrated low- or non-effectiveness of LMHW prophylaxis also in relation to the risk of bleeding complications^{3 4}. Therefore, there is a need for an alternative prophylaxis with documented effects.

In the perspective that different hospitals have different clinical traditions/indications for surgery of ATR and AF we have chosen to include both operated and non-operated ATR/AF, since both groups are equally served by VTE prophylaxis. Earlier studies have shown a just as high incidence of VTE in non-operated as in operated ATR/AF⁶, further indicating a benefit of demonstrating a VTE risk reduction in both operated/non-operated lower limb immobilized patients. Surgery vs. no surgery will be accounted for in the statistical analysis.

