Intervention: There is a need for new VTE prophylactic methods, especially in lower limb immobilized patients. IPC has been demonstrated cost effective both as adjuvant and versus no pharmacoprophylaxis in hospitalized patients by NICE. However, in an outpatient setting there are yet only recent short-term data of the efficacy of IPC. There is a need for data on the efficacy of IPC during long-term leg immobilization to inform guidelines.

The intervention, *addition of IPC to routine care*, will be administered in the emergency department or in the outpatient clinic. Patients will during the six weeks of lower limb immobilization receive bilateral calf IPC (Venaflo Elite, DJO LLC, Vista, CA, USA) applied under an orthosis (Aircast® AirSelect Elite, DJO LLC, Vista, CA, USA). This IPC-system delivers rapid inflation and graduated sequential compression. The IPC device is mobile and should therefore not restrict patient mobilization, but can be taken off if the patient wants to mobilize independently. The patients will be instructed to apply the IPC-therapy continuously, both day and night. Compliance with the treatment will be registered by both the patient and by the device⁹. American College of Chest Physicians recommend that efforts should be made to achieve 18 h of daily compliance with IPC in hospitalized patients¹⁷. However, there are no recommendations for mobile outpatients. Outpatients were in our recent study recommended at least 6h daily therapy, and in this study we will increase the recommendation to 10h/daily. Graduated compression stockings are part of IPC-care and these should be applied and worn under the IPC sleeves on both legs. IPC will be discontinued if the patient declines to continue IPC or had adverse effects of the IPC that warrants removal. At the 2 and 6 weeks visit the orthosis will be removed by a nurse and the patient will be examined by an orthopaedic surgeon (masked to the treatment allocation), who will document compliance and adverse events. At the 6 weeks visit the patient will also be sent for CDU-examination, which will document the main outcome. Patients will during the six weeks leg immobilization be weight-bearing with crutches or non-weight-bearing with crutches according to the preference of the orthopedic surgeon (masked to the treatment allocation). Weight-bearing will be recorded and accounted for in the statistical analysis.

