Outcome: The primary outcome, VTE at 6 weeks post-immobilization, will best be assessed by screening CDU of DVTs. CDU is rapidly becoming the investigation of choice to confirm the diagnosis of DVT since it is non invasive. It is acceptable to patients, can easily be repeated several times and uses equipment, which is widely available. Thus consent, accrual and adherence in a trial are likely to be more easily achieved than with alternatives.

The primary outcome will be validated by the explanatory outcome of VTE-prevention, assessed by quantification of blood flow, profibrinolysis and coagulation factors from blood serum taken by a study nurse at the 6 weeks visit.

A long-term effect of IPC on VTE and healing will be confirmed by the secondary patient-reported outcome measures (PROM). We have data suggesting that an asymptomatic DVT affects PROM at 1 year¹⁶. The PROM will be assessed by the patient filling in the validated questionnaires (EQ-5D-5L, ATRS, FAOS, OMAS) at the 1 year visit at the physiotherapist, who will also perform the functional evaluations, i.e. heel-rise tests. If any patient will miss the 1 year visit, the questionnaires will be sent home to the patient.

An IPC effect on tissue healing will be corroborated by assessment of callus production. Callus production in ATR and AF patients is assessed at 6 weeks by microdialysis followed by quantification of procollagens¹⁵.

To further control that the outcome measures are registered correctly, independent data monitoring and help with data management will be performed by eg. Karolinska Trial Alliance (KTA). Major outcome events (including serious adverse events believed to be due to treatment) will be supplied. All data will be reported using an online system registration at Karolinska Institutet called RedCap, which is a validated patient reporting tool used at over 300 universities.

Trial Organization: The Steering Committee will consist of [name] (PI), [name] (VTE expert), [name] (VTE expert), [name] (Radiologist, compression Doppler ultrasound), [name] (Statistician), [name] (coordinating study nurse), [name] (bone healing), [name] (expert on patient-reported outcome), and [name] (Patient representative).

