The randomisation form should be filed in the patient's medical notes, along with one copy of the signed informed consent form and patient brochure. The patient should receive a patient brochure along with a signed copy of the consent form. Copies should also be kept in the site file. The treatment allocation will be blinded for the assessors of outcome; i.e. ultrasonographers doing the CDU, physiotherapists or nurses performing the patient reported outcomes. The IPC-therapy will, due to its nature, not be blinded to the patient and the clinician applying the therapy.

Statistical analysis plan ([name], statistician)

All analyses will be based on intention to treat. We will analyze patients in the groups they are randomized to, regardless of treatment received. A patient might be withdrawn because of severe non-adherence or withdrawal of consent by the patient. For binary outcomes (e.g. occurrence of a primary or secondary outcome OR not), outcomes will be presented as odds ratios and 95% confidence intervals, adjusted using logistic regression for the factors used in the minimization algorithm and weight-bearing. We will calculate absolute reductions in risk from these values, as presented in the reference with similar study design²⁶.

Group differences for ordinal secondary outcome data, such as the patient-reported data (ATRS and OMAS), will be analyzed by nonparametric tests²⁰. Group differences for EQ5D-5L (index scale), FAOS (ratio scale) and continuous secondary outcome data will be analyzed by t-tests if the data are normally distributed, and using an appropriate nonparametric test otherwise.

Subgroup analyses will be performed to determine whether certain types of patients might gain greater or less benefit from IPC. We will estimate the effect of treatment allocation on the primary outcome subdivided by key baseline variables and adjusted for the other factors included in the minimization algorithm. Subgroup analyses will be performed by observing the change in log-likelihood when the interaction between the treatment and the subgroup is added into a logistic regression model. We will determine whether there is significant heterogeneity between these subgroups. The following preplanned subgroup analyses will be performed:

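### The only serious-adverse-event provision depends on believed relatedness, names no assessor, and leaves all-cause SAEs and deaths without a planned comparison by arm

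*Combined protocol and SAP*

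**What the plan says.** The one sentence on SAEs is in Study Design (PICO), Outcome, within the paragraph on data monitoring: "Major outcome events (including serious adverse events believed to be due to treatment) will be supplied". It does not say who forms the belief, to whom the events go, or what counts as treatment. No section defines an SAE.

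Non-serious and serious events overlap in the adverse-event list under Variables and measures. That list is introduced as "adherence to allocated treatment and adverse events related to IPC", assessed at 2 and 6 weeks, and has three items: "Any damage to the skin of the legs including infection"; "Any reasons for prematurely stopping the IPC"; and "Any fall associated with significant injury occurring within 6 weeks of enrollment". It adds that "The frequency of the adverse events of each group will be presented". The primary outcome, in the same section, includes symptomatic pulmonary embolism.

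On masking, the Intervention paragraph has the patient "examined by an orthopaedic surgeon (masked to the treatment allocation), who will document compliance and adverse events". The Comparator paragraph likewise gives adverse-event documentation to a surgeon described as masked. The patient-selection section says IPC will "not be blinded to the patient and the clinician applying the therapy".

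The Statistical analysis plan has no paragraph on safety.

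**The concern.** A relatedness criterion on entry turns a count of events into a count of judgements. In a trial where one arm has a device and the other has routine care, that judgement does not work alike in both arms. An event in an IPC patient can be blamed on the sleeve, and the same event in a control has no trial device to blame.

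Two things are at stake. First, supplied SAE counts could differ between arms when the true rates do not, or fail to differ when they do. Second, some events that matter here would seldom be attributed to IPC. Bleeding is the clearest example. The protocol argues against routine low molecular weight heparin partly because of bleeding, and the Comparator paragraph says pharmacological treatment starts when a VTE is found. If IPC reduces VTE, fewer IPC patients will receive anticoagulants, and bleeding could differ by arm in favour of IPC. Hardly anyone would call a control patient's bleed due to IPC, so the rule could miss a benefit as well as a harm. The protocol's opening section claims increased patient safety, and an all-cause table by arm is the evidence that claim would need.

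**Working it through.** **Step 1. Which serious events can be compared by arm?**

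| Event | Where covered | Conditional on attribution? | Comparable by arm? |
|---|---|---|---|
| Symptomatic pulmonary embolism | Variables and measures, primary outcome | No | Yes |
| Skin damage or infection | Variables and measures, adverse-event list | Item is worded as *any*; lead-in refers to IPC | Yes, if the item wording governs |
| Fall with significant injury, to 6 weeks | Same list | Same | Yes, if the item wording governs |
| Stopping IPC | Same list | Arises only with IPC | No |
| Death, reoperation, bleeding, other SAE | Only the SAE sentence in the Outcome paragraph | Yes | No, if judged unrelated |

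Follow-up for patient-reported outcomes runs to 12 months, but no adverse-event assessment is stated after week 6.

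**Step 2. Who applies the criterion?** The documents name no causality assessor. The surgeon who documents adverse events is described as masked in both arms. Someone who does not know the allocation cannot readily judge whether an event was due to IPC. In the IPC arm the same surgeon also documents compliance, whereas in the control arm a nurse does. So the judgement either needs knowledge of allocation or has no stated operator.

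**Step 3. The plan's own figure.** There is no SAE rate and no safety power statement to reproduce. The only figure needed is the sample size. For 28% versus 20%, two-sided alpha 0.05 and 90% power, the continuity-corrected formula gives 622 per arm; 2 × 622 = 1244, and 1244 / 0.90 = 1383 enrolled. Without the correction it is 597 per arm; 1194 / 0.90 = 1327. The planned 1400 is consistent with this, and 1:1 allocation gives 700 per arm.

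**Step 4. Illustration of the criterion.** Expected SAEs supplied per arm = n × p × a, where n = 700, p is the true all-cause SAE risk (assumed equal in both arms) and a is the share attributed to treatment. Assumed: a = 0.20 to 0.50 under IPC and 0 to 0.05 in controls.

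| p | True SAEs, IPC v control | Supplied, IPC | Supplied, control |
|---|---|---|---|
| 1% | 7 v 7 | 1.4 to 3.5 | 0 to 0.35 |
| 2% | 14 v 14 | 2.8 to 7 | 0 to 0.7 |
| 5% | 35 v 35 | 7 to 17.5 | 0 to 1.75 |

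For example, at 2%: 700 × 0.02 × 0.50 = 7, and 700 × 0.02 × 0.05 = 0.7. The direction follows entirely from the assumed shares. What does not depend on them is that a supplied count estimates the product p × a, and the plan provides nothing from which a could be known.

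**Step 5. What unfiltered counts would offer.** With 700 per arm and two-sided alpha 0.05 (normal approximation, pooled variance under the null), power to detect a doubling of all-cause SAEs is about 34% (1% v 2%), 59% (2% v 4%) and 95% (5% v 10%). Unless SAEs are fairly common, the gain is an undistorted description with an interval rather than a decisive test.

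**The case against.** The strongest reply has five parts.

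- **Masking.** A reader might infer that unblinded clinicians decide which SAEs are supplied. The documents do not say so. They call the clinician applying IPC unblinded but do not give that clinician the causality judgement, and they assign adverse-event documentation to a masked surgeon. This stands. What remains is that no assessor is named and that relatedness to IPC is hard to judge under masking.
- **Scope.** A reader might infer that serious harm cannot be compared at all. That is too strong: pulmonary embolism, skin damage or infection, and injurious falls can be counted in both arms, with frequencies promised for each group. This stands and narrows the gap to the last row of the Step 1 table.
- **Recording.** The sentence concerns what is supplied, and the one after it sends all data to the online system, so one cannot conclude that other SAEs go unrecorded. This stands in part. Nothing says they are recorded either, and the list of major outcome events extends only to SAEs thought to be caused by treatment.
- **Meaning of treatment.** The word is undefined and could cover surgery, cast, orthosis or heparin, so the control count is not near zero by construction. This stands; IPC is the natural reading, but the asymmetry is conditional on it.
- **Illustration.** The rates and shares are invented, and the plan specifies no test of supplied SAEs. This stands. It would also be wrong to conclude that a harmless device and one that doubles SAEs must give the same table. That needs the attributed share to halve as the rate doubles (14 × 0.50 = 28 × 0.25 = 7). With the share held at 0.50, the counts are 7 and 14.

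**Conclusion.** The point holds as a gap in safety capture and reporting. The sole SAE provision is conditional on believed relatedness, has no named assessor, and is not backed by any planned all-cause tabulation of SAEs and deaths by arm. Deaths, reoperations, bleeding and other SAEs judged unrelated therefore cannot be compared from the plan as written.

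That conclusion rests on the text alone. The further statement that supplied counts would probably be unequal under equal true rates assumes that *treatment* means IPC and that attribution is more frequent in the IPC arm. Its size cannot be derived from the documents, and the 2.8–7 versus 0–0.7 range is an illustration only. The primary efficacy analysis is not affected. The change should be made, because events not collected prospectively may not be reliably recoverable later.

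**What to change.** In the Outcome paragraph, replace the SAE wording inside the parenthesis with: *all deaths and all serious adverse events in both arms, from randomisation to the end of follow-up, whatever their believed cause*. Add a definition of an SAE and say who receives the reports.

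Record relatedness as a separate field that does not decide whether an event is supplied. State who judges it and under what masking.

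Add to the Statistical analysis plan a table of all SAEs and deaths by randomised arm for the final report.

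The cost is a protocol amendment of a few sentences, one form in the online system and one table. Sites will complete somewhat more SAE forms, including for unrelated events. No treatment or visit changes.

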Comparator: Since there are no documented highly effective therapies for DVT reduction during leg immobilization, and guidelines vary regarding prophylaxis, we chose to use treatment-as-usual as a comparator, regardless of LMHW use or not^{3 4}. Based on our calculations less 10% of the patients will receive LMHW in clinical practice and our power calculations has taken this into account. NICE has stated that LMWH is not a feasible general treatment, especially health economically, during six weeks for all patients with leg immobilization. One review, including 1,490 patients from six randomized trials, showed a small reduction in DVTs using LMHW⁸. However, they concluded that more research is needed to develop more effective and safe thromboprophylactic treatments. Moreover, since a study with LMHW as a comparator would necessitate too many patients - this was not an option. The main research question remains: Is adjuvant IPC more effective than routine care for reducing the incidence of VTE in patients during lower limb immobilization? The usage of no general VTE-prevention in the comparator group is moreover justified since a DVT-screening will be performed on all patients. LMWH vs. no LMWH will be accounted for in the statistical analysis. If a VTE is detected we will follow clinical guidelines and initiate

pharmacological VTE-treatment.

The comparator, **routine care**, lower limb immobilization will be administered by normal routine in the emergency department or in the outpatient clinic. Routine care include that the lower limb will be immobilized in an orthosis or a below-knee plaster cast according to local routines. At the 2 and 6 weeks visit the orthosis/plaster cast will be removed by a nurse who will document compliance. Subsequently, the patient will be examined by an orthopaedic surgeon (masked to the treatment allocation), who will document adverse events. At the 6-8 weeks visit the patient will also be sent for CDU-examination, which will document the main outcome. Patients will during the six weeks leg immobilization be weight-bearing with crutches or non-weight-bearing with crutches according to the preference of the orthopedic surgeon (blinded to the treatment group). Weight-bearing will be recorded and accounted for in the statistical analysis.

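### Read literally, the SAP's adjusted odds-ratio rule covers adverse events, where sparse counts make it infinite or very wide, and no interval is planned for the absolute difference in harm

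*Combined protocol and SAP*

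**What the plan says.** The Statistical analysis plan has one rule for binary data, whether primary or secondary: "outcomes will be presented as odds ratios and 95% confidence intervals, adjusted using logistic regression for the factors used in the minimization algorithm". Weight-bearing is named as a further covariate. The next sentence adds: "We will calculate absolute reductions in risk from these values, as presented in the reference with similar study design". Two other places add covariates: "Surgery vs. no surgery will be accounted for in the statistical analysis" (Study Design, Patients) and "LMWH vs. no LMWH will be accounted for in the statistical analysis" (Comparator). The minimization factors are never listed.

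Variables and measures brings adverse events under this rule: "Further patient data that will be analyzed as secondary outcome measures at 2 and 6 weeks are adherence to allocated treatment and adverse events". It labels them binary and names three: skin damage to the legs including infection, reasons for stopping IPC early, and "Any fall associated with significant injury occurring within 6 weeks of enrollment". It also says that their frequency will be presented for each group.

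The SAP makes no exception for adverse events and names no method for sparse binary data. For continuous outcomes it does give a fallback, a nonparametric test when normality fails.

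**The concern.** A logistic model estimates a finite treatment odds ratio only if both arms contain events. If one arm has none, the maximum-likelihood estimate is zero or infinite. With a handful of events it is finite but so imprecise that it bounds nothing, and extra covariates make the fit more fragile.

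The three adverse events differ in how they meet this problem. Early stopping of IPC cannot occur in a patient who was not given IPC, so the between-arm odds ratio has no meaning there. Injurious falls may be rare. Skin damage may or may not be.

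The protocol presents IPC as a way to raise patient safety (Purpose and Aims) and cites a need for safer prophylaxis (Survey of the Field). A reader will therefore want to know how large an excess of falls or skin damage the data can exclude. That takes an interval for the absolute difference, and none is specified.

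**Working it through.** **Inputs.** At least 1400 patients with 10% drop-out (Estimated sample size and power) and 1:1 allocation (Study Design): 1400 × 0.90 = 1260, or 630 per arm. As a check on this reading, 630 per arm at 28% vs 20% with two-sided alpha 0.05 (sidedness is not stated) gives 91.5% power, against the plan's 90%. No adverse-event rate is stated, so the rates below are assumptions.

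**1. Early stopping of IPC.** The control count is 0 by design, barring crossover. The odds ratio has 0 in its denominator, so it is infinite whatever the rate in the IPC arm. No rate assumption is needed.

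**2. Chance of a zero-event arm for falls or rare skin damage.** With the same rate p in both arms, P(at least one arm has no event) = 1 − (1 − (1 − p)^630)².

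| p per arm | (1 − p)^630 | P(zero-event arm) |
|---|---|---|
| 0.2% | 0.283 | 49% |
| 0.3% | 0.151 | 28% |
| 0.5% | 0.0425 | 8.3% |
| 1% | 0.0018 | 0.4% |

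If IPC doubles the rate, the chance is 17% at a control rate of 0.3%, 4% at 0.5% and 0.2% at 1%. At 0.2% vs 0.4%, the chance of no control event but at least one IPC event is 0.283 × (1 − 0.996^630) = 0.283 × 0.920 = 26%.

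**3. Precision when both arms have events.** In 1000 simulated trials per scenario, the model held treatment plus six assumed binary covariates: injury type, surgery, age 40 or over, prior DVT, LMWH and weight-bearing. The covariates and their prevalences are assumptions, because the minimization factors are not listed. The table gives the median ratio of the upper to the lower 95% limit of the adjusted odds ratio.

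| Control rate | Risk ratio 1 | Risk ratio 2 |
|---|---|---|
| 0.3% | 83 | 37 |
| 0.5% | 28 | 18 |
| 1% | 10 | 7 |
| 2% | not run | 4.0 |

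At least one coefficient diverged in 78–96% of trials at 0.3–0.5% and in 15% at 2% with risk ratio 2. It was often a covariate's coefficient, which does not by itself make the treatment odds ratio infinite.

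**4. Absolute reductions derived from the odds ratio.** The SAP does not give the conversion. The usual one is p1 = OR × p0 / (1 − p0 + OR × p0). With p0 = 0 and OR infinite, the product OR × p0 is indeterminate. With a finite but very wide odds ratio, the derived difference is correspondingly unstable.

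**5. The alternative on illustrative counts, 630 per arm (IPC vs control).**

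| Falls | Odds ratio (exact 95% CI) | Risk difference, points (Newcombe 95% CI) |
|---|---|---|
| 6 vs 0 | infinite (1.18 to infinity) | +0.95 (0.16 to 2.06) |
| 6 vs 2 | 3.0 (0.54 to 30.7) | +0.63 (−0.34 to 1.77) |

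The risk difference has a finite upper bound on harm in both cases.

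**The case against.** The strongest reply is that adverse events have their own presentation rule in Variables and measures, frequency per group. A mainly descriptive report is therefore a reasonable reading, and the SAP's binary rule may never have been meant for them. Turning to exact or penalised methods when events prove sparse is also routine. This has force, but it does not close the gap: on that reading no between-group interval for harm is planned at all.

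A reader might infer that the plan hides absolute harm or has no usable measure of it. The documents do not support that. Frequencies per group are promised, the sentence after the odds-ratio rule promises absolute reductions, and anyone with the counts could compute a risk-difference interval.

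A reader might also infer that the odds-ratio interval is undefined when one arm is empty. The SAP does not prescribe Wald limits, and an exact interval exists. In the 6 vs 0 example it has an informative lower limit but no upper one.

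The size of the problem for falls and skin damage rests on an assumed rate. Nothing shows that skin damage, a broad category in a trial that includes operated patients, is rare, and at about 1% per arm or more an empty arm is unlikely. Nor do the documents support a fixed minimum event count for adjusted models, such as 50. The covariate set is unlisted, and the simulated interval at 2% vs 4% (about 38 expected events) was already usable.

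Finally, the safety case in the protocol is made mainly against drug prophylaxis and bleeding, and no recommendation hangs on the adjusted odds ratio for falls.

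**Conclusion.** The point holds as a minor gap in the SAP. For early stopping of IPC, the stated rule gives an infinite odds ratio with no assumption beyond controls not receiving IPC. For injurious falls, and for skin damage only if it is rare, it may give an infinite or very wide one: a zero-event arm has probability 49% at an assumed 0.2% per arm, 8% at 0.5% and under 1% at 1%, with 630 per arm. Even at 1%, the upper limit of the adjusted odds ratio is typically seven to ten times the lower, under the assumed covariates.

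Absolute figures are planned. What is missing is a stable way to obtain the difference and a confidence interval for it. That holds whether the SAP's rule or the frequency sentence governs. The primary analysis and the sample size are untouched.

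**What to change.** In the Statistical analysis plan, add a sentence exempting adverse events from the adjusted logistic rule:

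- For injurious falls and skin damage, report counts per arm and the unadjusted risk difference with a Newcombe or exact 95% confidence interval. An exact or Firth odds ratio may be added.
- Report premature stopping of IPC descriptively, in the IPC arm only, with no between-arm comparison.
- Keep the per-group frequencies already promised, and set no event-count threshold.

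The change needs no new data or patients. Its small cost is that adverse-event comparisons lose covariate adjustment. That includes weight-bearing, which follows the surgeon's preference during immobilization and so is not simply a baseline factor that randomisation balances.

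### The primary model adjusts for weight-bearing, which may be measured after allocation; if allocation changes it, the intention-to-treat odds ratio and the risk reduction derived from it are biased

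*Combined protocol and SAP*

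**What the plan says.** **The model.** Under Statistical analysis plan, all analyses are by intention to treat. Results for binary outcomes are odds ratios "adjusted using logistic regression for the factors used in the minimization algorithm and weight-bearing", and absolute risk reductions are calculated from those results. Weight-bearing is named in addition to the minimisation factors, so it is not one of them.

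**When weight-bearing happens.** Under Material: Patient selection, the allocation is issued at the end of the web randomisation session, once baseline data have been entered. The Intervention paragraph of Study Design (PICO) then says: "Patients will during the six weeks leg immobilization be weight-bearing with crutches or non-weight-bearing with crutches". The choice follows the "preference of the orthopedic surgeon (masked to the treatment allocation). Weight-bearing will be recorded and accounted for in the statistical analysis". The Comparator paragraph says the same for controls and calls the surgeon blinded. Neither paragraph says when weight-bearing is recorded, or whether the prescribed regimen or actual behaviour is meant.

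**How the subgroup text treats it.** The paragraph on patients at higher risk of DVT expects weight-bearing to affect DVT risk and groups it with factors present at baseline.

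**Other covariates.** The Comparator paragraph states that "LMWH vs. no LMWH will be accounted for in the statistical analysis". The Patients paragraph makes the same promise for surgery. Neither says how this will be done or when the variable is measured.

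**The concern.** The research question is the effect of adding IPC to routine care, which under intention to treat is the total effect of allocation. A covariate fixed before allocation leaves that target intact. A covariate that allocation can change does not. Adjusting for it removes any part of the effect that runs through it. It also opens a non-causal association if the covariate and VTE share an unmeasured cause such as injury severity.

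Bias therefore needs two links. The plan itself grants the first, that weight-bearing is related to DVT. The second, that allocation affects weight-bearing, is not shown, but three features of the design leave it open:

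- Patients and the clinician applying IPC are not blinded, and the device "can be taken off if the patient wants to mobilize independently".
- The IPC arm wears an orthosis, whereas controls have an orthosis or a plaster cast.
- The masking of the surgeon is uncertain. In the IPC arm the patient is "examined by an orthopaedic surgeon (masked to the treatment allocation), who will document compliance and adverse events", whereas for controls "the orthosis/plaster cast will be removed by a nurse who will document compliance". A surgeon who records compliance with a device used in only one arm may learn the allocation.

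At stake are the primary odds ratio and the absolute reduction, which will be read against the plan's minimum clinically relevant reduction of 4 points.

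**Working it through.** **Inputs from the plan** (Estimated sample size and power): at least 1400 patients, 1:1, 10% drop-out, so 1400 × 0.90 / 2 = 630 evaluable per arm; VTE 28% vs 20%; alpha 0.05, taken as two-sided.

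**Assumed inputs** (not in the documents): 50% weight-bearing in controls; 30% to 70% in the IPC arm; weight-bearing odds ratio for VTE of 0.5, with 0.7 as a weaker case; no other covariates.

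**The plan's own figure.** Two proportions, 28% vs 20%, 90% power: 597 per arm, and 1194 / 0.90 = 1327. With continuity correction: 622 per arm, and 1244 / 0.90 = 1383, close to 1400. Power with 630 per arm is 91.5% by the two-proportion formula and 91.2% by the Wald test on the log odds ratio. The stated 90% is reproduced, and this point does not affect it. The target odds ratio is (0.20/0.80) / (0.28/0.72) = 0.643.

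**Method.** The model is logit P(VTE) = a + b·IPC + c·WB. With c fixed, solve for each arm's intercept so that its overall risk meets the target:

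q·expit(a + c) + (1 − q)·expit(a) = p

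Here q is the arm's weight-bearing share and p its VTE risk. Then b = a(IPC) − a(control).

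**Worked case: c = ln 0.5 = −0.693, 50% vs 60% weight-bearing.**

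1. Control: 0.5·expit(a − 0.693) + 0.5·expit(a) = 0.28 gives a = −0.624.
2. IPC: 0.6·expit(a − 0.693) + 0.4·expit(a) = 0.20 gives a = −1.005.
3. b = −0.381, so the adjusted odds ratio is 0.683.
4. Applied to the 28% control risk: odds 0.389 × 0.683 = 0.266, risk 21.0%, reduction 7.0 points against a true 8.0.
5. The SE of b, from the expected information with 630 per arm, is 0.135. Power = Φ(0.381/0.135 − 1.96) ≈ 80%.

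**All cases, weight-bearing odds ratio 0.5**

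| IPC minus control, weight-bearing (points) | OR, true 28% vs 20% | Reduction (points; true 8.0) | OR, no true effect |
|---|---|---|---|
| −20 | 0.558 | 10.2 | 0.874 |
| −10 | 0.595 | 9.2 | 0.934 |
| −5 | 0.615 | 8.7 | 0.966 |
| 0 | 0.637 | 8.2 | 1.000 |
| +5 | 0.659 | 7.6 | 1.036 |
| +10 | 0.683 | 7.0 | 1.074 |
| +20 | 0.736 | 5.8 | 1.155 |

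The 0.637 at no difference, against 0.643, is non-collapsibility of the odds ratio and not bias. With a weight-bearing odds ratio of 2.0 the true-effect columns are mirrored. If the reduction is instead standardised to the pooled weight-bearing share, the range is 5.4 to 10.4 points, and exactly 8.0 at no difference.

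**Power**, true 28% vs 20%: 92% at no difference, 80% at +10, 61% at +20.

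**No true effect.** The apparent result runs from a 2.6-point reduction (−20) to a 3.0-point increase (+20). The chance of a false significant benefit is 2.5% at no difference, 4.6% at −5, 7.8% at −10 and 18% at −20.

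**Weaker case, weight-bearing odds ratio 0.7.** From −20 to +20 the odds ratio runs 0.598 to 0.690 (true 0.643) and 0.932 to 1.075 (null). False benefit is 3.4%, 4.7% and 7.9% at −5, −10 and −20. Power is 89%, 86% and 78% at +5, +10 and +20.

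**Shared cause only.** Suppose weight-bearing has no effect of its own, but a standard normal severity factor lowers weight-bearing and raises VTE. Over the same −20 to +20 range the null odds ratio becomes 0.956 to 1.047 at 0.5 logit per SD, and 0.868 to 1.162 at 1 logit per SD.

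**The case against.** The strongest reply is that the covariate is a prescribed regimen, chosen by a surgeon who does not know the allocation. The reference to the six weeks then says when the regimen applies, not when it is chosen or recorded, and the subgroup text calling it a baseline factor fits. On that reading the sections agree and there is no bias. The Intervention paragraph also says that the device is mobile and should not restrict mobilisation, so an arm difference is not intended. Taking the device off to move about is not the same as changing the regimen, and no section says that a cast changes weight-bearing. The largest figures above need a 20-point arm difference together with an odds ratio of 0.5, and a masked prescriber makes that hard to motivate. LMWH and surgery are not named in the model. Since the minimisation factors are not listed, either could be one of them.

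Much of this stands. The benign reading is possible, masking makes a large shift less likely, and small shifts do modest harm: 5 points move the reduction to 7.6 or 8.7. But the text does not secure that reading. Masking protects the prescription, not what an unblinded patient does, and nothing says that the prescription is what enters the model. The point about LMWH and surgery applies only if accounting for them means covariate adjustment.

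**Conclusion.** The concern holds, as a conditional statement. The plan puts into its primary model a covariate that it describes in one place as occurring after allocation and in another as baseline. It fixes no measurement before allocation and plans no analysis without the covariate. Bias in the intention-to-treat estimate follows if allocation changes weight-bearing and weight-bearing is associated with VTE. It can go either way, and it is absent if allocation does not change weight-bearing.

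Confidence is high in the inconsistency and in the conditional bias, not in any particular size, because the documents give no weight-bearing rates or effects. Under the assumptions used, a 10-point arm difference moves the absolute reduction by about 1 point. A 20-point difference moves it by a little over 2 points, against a minimum relevant reduction of 4. This should be corrected before the primary analysis. The sample size is unaffected.

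**What to change.** - Restrict the primary model to treatment and variables fixed before allocation: the minimisation factors, plus the intended weight-bearing regimen only if it was recorded before allocation. Derive the absolute risk reduction from that model.
- Report observed weight-bearing by arm descriptively. Show the model adjusted for it only as a labelled sensitivity analysis.
- Use weight-bearing as a subgroup factor only if it was recorded before allocation.
- Apply the same rule to LMWH and surgery wherever accounting for them means covariate adjustment.
- Reconcile the Patients, Intervention and Comparator paragraphs with the Statistical analysis plan and its subgroup text.

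If weight-bearing is already recorded before allocation, a sentence giving its definition and time point settles the main issue.

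**Cost.** Protocol and SAP wording only, with no new visits or measurements. Any precision gained from observed weight-bearing leaves the primary model. In the illustration with no arm difference and an odds ratio of 0.5, power falls from 91.7% to 91.2%. For patients already randomised, an intended regimen not recorded before allocation cannot be recovered. In that case the primary model omits weight-bearing.
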